4.9.4 Secondary Efficacy Endpoints Analysis for Phase 1b/2a/Biomarker Cohort

4.9.4.1 Objective Response Rate per RECIST 1.1 and iRECIST as determined by the Investigator for Biomarker Cohort

The same definition is followed as that for primary endpoint.

Exact two-sided 95% CIs for the ORR/iORR will be calculated using Clopper-Pearson method.

In addition, the following figures will be provided for each phase/arm, as applicable.

- Waterfall plot for best percentage change of target lesion size from baseline (maximum decrease, or minimum increase if no decrease)
- Swimmer plot for treatment duration and response
- Spider plot for the change of target lesion from baseline

4.9.4.2 Disease Control Rate per investigator

DCR per RECIST 1.1 is defined the proportion of subjects with confirmed CR, confirmed PR, SD (minimum duration of 4 weeks from the first dose of study drugs to the date of last non PD/NE) as BOR in efficacy evaluable analysis set.

iDCR per iRECIST is defined the proportion of subjects with iCR, iPR, iSD as iBOR in efficacy evaluable analysis set.

Exact two-sided 95% CIs for the DCR/iDCR will be calculated using Clopper-Pearson method.

4.9.4.3 Duration of Response and Progression Free Survival per investigator

DoR per RECIST 1.1

For subjects who achieve confirmed CR or PR as BOR, DoR is defined as the time (months) from the date of the first CR/PR to the date of the documented disease progression or death, whichever occurs first. The subjects without progression and alive will be censored according to censor rule.

Censoring rules for DoR are the same as those of PFS (Table 4).

iDoR per iRECIST

For subjects who achieve iCR or iPR as BOR, iDoR is defined as the time (months) from the date of the first iCR/iPR to the date of the first iUPD that is followed by iCPD without interruption by iSD/iPR/iCR or death, whichever occurs first. The subjects without iCPD and alive will be censored on the date of last assessment (including iUPD). Censoring rules for DoR are the same as those of PFS (Table 5).

DoR/iDoR median values and its two-sided 95% CIs will be estimated using Kaplan-Meier (KM) method. The DoR/iDoR event-free rates at 3 and 6 months if applicable and the associated two-sided 95% CIs will also be estimated using KM method.

Progression free survival (PFS) per RECIST 1.1

PFS is defined as the time (months) from the date of the first dose of study drugs to the date of the documented disease progression or death, whichever occurs first. The subjects without progression and alive will be censored on the date of last assessment.

Progression free survival (PFS) per iRECIST

iPFS is defined as the time (months) from the date of the first dose date of study drugs to the date of the first iUPD that is followed by iCPD without interruption by iSD/iPR/iCR or death, whichever occurs first. The subjects without iCPD and alive will be censored on the date of last assessment (including iUPD).

PFS/iPFS median values and its two-sided 95% CIs will be estimated using KM method. The PFS/iPFS event-free rates at 3 and 6 months if applicable and the associated two-sided 95% CIs will also be estimated using KM method.

PFS/iPFS of each DL in Phase 1a and each arm in Phase 2a will be plotted with KM curve.

Table 4 Censoring and Event rules for DoR and PFS per RECIST 1.1

Situation	Date of Progression or Censoring	Outcome
No PD or death at the time of data cutoff	Date of last adequate disease assessment	Censored
Start a new anti-cancer therapy before death or PD	Date of last adequate disease assessment prior to the date of new anti-cancer therapy	Censored
Death or PD after two or more missing consecutive assessments	Date of last adequate disease assessment before missing two or more consecutive assessments	Censored
1 missed disease assessments before Death or PD	Date of Death or PD, whichever is first	Event
Death or PD before or no new anti-cancer therapy	Date of Death or PD, whichever is first	Event

Table 5 Censoring and Event rules for iDoR and iPFS per iRECIST

Situation	Date of Progression or Censoring	Outcome
No iCPD or death at the time of data cutoff	Date of last adequate disease assessment	Censored
Start a new anti-cancer therapy before death or iCPD	Date of last adequate disease assessment prior to the date of new anti-cancer therapy	Censored
Death or iCPD after two or more missing consecutive assessments	Date of last adequate disease assessment before missing two or more consecutive assessments	Censored
1 missed disease assessments before death or iCPD	Date of the (1) first iUPD that is followed by iCPD without interruption by iSD/iPR/iCR, (2) date of iCPD if no immediate prior iUPD, or (3) death, whichever occurs first	Event
Death or iCPD before/ or no new anti-cancer therapy	Date of the (1) first iUPD that is followed by iCPD without interruption by iSD/iPR/iCR, (2) date of iCPD if no immediate prior iUPD, or (3) death, whichever occurs first	Event

All efficacy data including target/non-target/new lesions measurement will be listed.

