## 5.7. Study Schema

## 5.8. Treatment Schema

Radiological tumor assessments will be conducted every 2 cycles (6 weeks  $\pm$ 1 week) during the first 6 months, and every 3 cycles (9 weeks  $\pm$ 1 week) thereafter. Confirmatory scans must be performed at >4 weeks after initial assessment of response to confirm a best response of CR or PR, whenever disease progression is suspected (e.g., symptomatic deterioration), and at End of Treatment visit. If disease progression is identified by RECIST 1.1, a second scan will be scheduled 4-8 weeks later to confirm disease progression by iRECIST. (See Section 13 and Appendix A for details).

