#### 6.5. Study Treatment Beyond Progression

Immunotherapeutic agents may produce antitumor effects by potentiating endogenous cancer-specific immune responses. The response patterns seen with such an approach may extend beyond the typical time course of responses seen with cytotoxic agents and can manifest as a clinical response after an initial increase in tumor burden or even the appearance of new lesions.

At the investigator's discretion, a participant may continue on study intervention beyond radiological progression as defined by RECIST 1.1 if the clinical condition of the participant is stable or the participant is improving symptomatically, and the investigator expects continued clinical benefit for the participant until subsequent progression determined by iRECIST criteria ([Appendix A – Assessment of Disease](#)).

In participants who have initial evidence of radiological PD by RECIST 1.1, it will be at the discretion of the investigator whether or not to continue a participant on study treatment until repeat imaging is obtained to determine whether participant's disease is progressing or the initial evidence represents a 'pseudoprogression or tumor flare'. This clinical judgment decision should be based on the participant's overall clinical condition, including performance status, clinical symptoms, and laboratory data. Participants may continue to receive study treatment until tumor assessment is repeated  $\geq 4$  weeks later in order to confirm PD by iRECIST.

Per iRECIST ([Appendix A – Assessment of Disease](#)) disease progression should be confirmed by the site in 4 to 8 weeks after site-assessed first radiologic evidence of PD in clinically stable participants. Participants who have unconfirmed disease progression may continue on treatment at the discretion of the investigator until progression is confirmed by the site, provided they have met the clinically stable definition as [Appendix A – Assessment of Disease](#), including. absence of

symptoms and signs indicating clinically significant progression of disease. Subjects should remain on the study and continue to be monitored according to the Schedule of Assessments.

Any participant deemed clinically unstable should be discontinued from study treatment at site-assessed first radiologic evidence of PD, and is not required to have repeat tumor imaging for confirmation of PD by iRECIST.

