### iRECIST Assessment of Disease

iRECIST is based on RECIST 1.1 but adapted to account for the unique tumor response seen with immunotherapeutic drugs. iRECIST will be used by the Investigator to assess tumor response and progression and make treatment decisions. When clinically stable, subjects may continue study intervention beyond RECIST 1.1 progression with continued assessment of response according to the rules outlined in [Table 6](#). iRECIST reflects that some subjects can have a transient tumor flare in the first few months after the start of immunotherapy, and then experience subsequent disease response. This data will be captured in the clinical database.

- If subject is clinically stable, continue study intervention per protocol
  - Perform scans 4 to 8 weeks after RECIST 1.1 progression
  - Continue investigator assessment per iRECIST
- If the subject is not clinically stable, best medical practice is to be applied.

For the purpose of this decision process, lack of clinical stability is defined as:

- Unacceptable toxicity
- Clinical signs or symptoms indicating clinically significant disease progression
- Decline in performance status
- Rapid disease progression or threat to vital organs or critical anatomical sites (e.g., CNS metastasis, respiratory failure due to tumor compression, spinal cord compression) requiring urgent alternative medical intervention.

Any subject deemed **clinically unstable** should be discontinued from study treatment at site-assessed first radiologic evidence of PD and is not required to have repeat tumor imaging for confirmation of PD by iRECIST.

[figure not shown]
If the Investigator decides to continue treatment, the subject should continue to receive study treatment. Regardless of the subject is on treatment or off treatment, the tumor assessment should be repeated 4 to 8 weeks later to confirm PD by iRECIST, per Investigator assessment.

If repeat imaging does not confirm PD per iRECIST, as assessed by the Investigator, and the subject continues to be clinically stable, study treatment may continue and follow the regular imaging schedule. If PD is confirmed, subjects will be discontinued from study treatment.

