**Table 6: Imaging and treatment after first radiologic evidence of progressive disease**

	Clinically Stable		Clinically Unstable	
	Imaging	Treatment	Imaging	Treatment
First radiologic evidence of PD by RECIST 1.1	Repeat imaging at 4 to 8 weeks to confirm PD.	May continue study treatment at the Investigator's discretion while awaiting confirmatory tumor imaging by site by iRECIST.	Repeat imaging at 4 to 8 weeks to confirm PD per Investigator's discretion only.	Discontinue treatment
Repeat tumor imaging confirms PD (iCPD) by iRECIST per Investigator assessment	No additional imaging required.	Discontinue treatment (exception is possible upon consultation with Sponsor).	No additional imaging required.	Not applicable
Repeat tumor imaging shows iUPD by iRECIST per Investigator assessment	Repeat imaging at 4 to 8 weeks to confirm PD. May occur at next regularly scheduled imaging visit.	Continue study treatment at the Investigator's discretion.	Repeat imaging at 4 to 8 weeks to confirm PD per Investigator's discretion only.	Discontinue treatment
Repeat tumor imaging shows iSD, iPR, or iCR by iRECIST per Investigator assessment.	Continue regularly scheduled imaging assessments.	Continue study treatment at the Investigator's discretion.	Continue regularly scheduled imaging assessments.	May restart study treatment if condition has improved and/or clinically stable per Investigator's discretion. Next tumor imaging should occur according to the regular imaging schedule.

iCPD = iRECIST confirmed progressive disease; iCR = iRECIST complete response; iRECIST = modified Response Evaluation Criteria in Solid Tumors 1.1 for immune-based therapeutics; iSD = iRECIST stable disease; iUPD = iRECIST unconfirmed progressive disease; PD = progressive disease; RECIST 1.1 = Response Evaluation Criteria in Solid Tumors 1.1.; VOP=verification of progression

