### *Assessment and Decision at RECIST 1.1 Progression*

For subjects who show evidence of radiological PD by RECIST 1.1 as determined by the Investigator, the Investigator will decide whether to continue a subject on study treatment until repeat imaging is obtained (using iRECIST for subject management (see [Table 6](#) and [Figure 5](#))). This decision by the Investigator should be based on the subject's overall clinical condition. Clinical stability is defined as the following:

- Absence of symptoms and signs indicating clinically significant progression of disease
- No decline in ECOG performance status
- No requirements for intensified management, including increased analgesia, radiation, or other palliative care

Any subject deemed **clinically unstable** should be discontinued from study treatment at site-assessed first radiologic evidence of PD and is not required to have repeat tumor imaging for confirmation of PD by iRECIST.

If the Investigator decides to continue treatment, the subject may continue to receive study treatment and the tumor assessment should be repeated 4 to 8 weeks later to confirm PD by iRECIST, per Investigator assessment.

Tumor flare may manifest as any factor causing radiographic progression per RECIST 1.1, including:

- Increase in the sum of diameters of target lesion(s) identified at baseline to  $\geq 20\%$  and  $\geq 5$  mm from nadir
  - **Note:** the iRECIST publication uses the terminology “sum of measurements”, but “sum of diameters” will be used in this protocol, consistent with the original RECIST 1.1 terminology.
- Unequivocal progression of non-target lesion(s) identified at baseline
- Development of new lesion(s)

iRECIST defines new response categories, including iUPD (unconfirmed progressive disease) and iCPD (confirmed progressive disease). For purposes of iRECIST assessment, the first visit showing progression according to RECIST 1.1 will be assigned a visit (overall) response of iUPD, regardless of which factors caused the progression.

At this visit, target and non-target lesions identified at baseline by RECIST 1.1 will be assessed as usual.

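### iPFS censors living subjects at an unconfirmed iUPD, although the protocol does not require the confirming scan in clinically unstable subjects; this biases iPFS upward (minor)

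*SAP*

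**What the plan says.** SAP 4.9.4.3 recognises two events for iPFS and iDoR: a first iUPD that leads to iCPD without an intervening iSD, iPR or iCR, and death. For everyone else, "The subjects without iCPD and alive will be censored on the date of last assessment (including iUPD".

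Table 5 has no row that makes an unconfirmed iUPD an event. Two of its rows censor at an earlier adequate assessment, which can be the iUPD scan itself: "Start a new anti-cancer therapy before death or iCPD" and "Death or iCPD after two or more missing consecutive assessments".

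The protocol differs on whether a confirming scan will exist:

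- Section 6.5 takes a clinically unstable participant off treatment "at site-assessed first radiologic evidence of PD, and is not required to have repeat tumor imaging for confirmation of PD by iRECIST".
- Appendix A, Assessment and Decision at RECIST 1.1 Progression, repeats that such a subject "is not required to have repeat tumor imaging for confirmation of PD by iRECIST".
- Table 6, clinically unstable column: "Repeat imaging at 4 to 8 weeks to confirm PD per Investigator's discretion only".
- Section 5.8, with the same text in the synopsis, states for any RECIST 1.1 progression that "a second scan will be scheduled 4-8 weeks later to confirm disease progression by iRECIST".
- Appendix A, iRECIST Assessment of Disease, contains the exemption and also says "Regardless of the subject is on treatment or off treatment, the tumor assessment should be repeated 4 to 8 weeks later".

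Section 13.2 and SAP 4.9.1 end imaging once the investigator identifies progression. Section 13.3 asks for later imaging only where progression was not documented. Sections 6.4.1 and 6.6 continue scans unless progression is by both RECIST 1.1 and iRECIST.

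**The concern.** Kaplan-Meier estimation assumes that a censored subject has the same outlook as those still at risk. Here a subject can be censored at the scan that showed progression, because he or she was too unwell to be scanned again. Such subjects are represented by others who are doing better, so the curve is too high.

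A later death does not fully repair this. It counts at the death date, not at the iUPD date. If two scans count as missed first, the death is censored back. Table 5 does not say whether a scan is missing once imaging is no longer due, so two programmers could produce different curves from the same data.

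At stake are the iPFS medians, the 3- and 6-month rates and the curves for each arm, and iDoR where an affected subject had responded.

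**Working it through.** The plan states no expected iPFS, event count or censoring rate, so there is no figure of its own to reproduce. The checks below give direction and an order of size.

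**1. One subject, exact.** Take 25 at risk and 9 iUPDs at the week-6 scan. Counting all nine gives 16/25 = 64%. Censoring one gives 17/25 = 68%. Sixteen subjects remain at risk either way, so every later value is multiplied by 68/64 = 17/16 = 1.06.

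**2. Closed form.** Scans fall at weeks 6, 12, 18 and 24 (protocol 13.2). The 9-week median is an assumption; protocol 2.1.6 cites 2.1 months for pembrolizumab alone in ovarian cancer. With exponential progression, the chance of progressing between scans is h = 1 - 0.5^(6/9) = 0.370. If a share u of progressors is censored at the iUPD scan and no later death is counted, each scan contributes a factor 1 - (1 - u)h.

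| u | Factor per scan | 6-month rate (factor^4) |
|---|---|---|
| 0 | 0.630 | 15.7% |
| 10% | 0.667 | 19.8% |
| 20% | 0.704 | 24.6% |

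The overstatement is about 4 and 9 points. This is the case in which every unconfirmed subject starts new therapy.

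**3. Simulation with deaths.** Further assumptions: 7% of rescanned first progressions resolve (the melanoma figure in SAP 1.4, borrowed here); median survival after progression is 6 to 20 weeks; unconfirmed subjects are censored at iUPD unless they die before a second missed scan. There are 200,000 subjects per scenario, read at week 26. RECIST 1.1 PFS is about 15.7%. Correct iPFS, with each true progression counted at its first iUPD, is about 18%.

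| Unconfirmed share | 6-month iPFS, SAP rule | Overstatement (points) |
|---|---|---|
| 10% | 20.1-21.6% | 1.7-3.1 |
| 20% | 21.6-24.7% | 3.5-6.5 |

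A separate simulation used a 2.1-month median, no pseudo-progression, scan windows, 0 or 30% switching therapy and both readings of a missed scan. Against a reference of 16%, it gave 18-21% at a 10% share and 21-26% at 20%.

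**4. Effect of the undefined word.** If scans no longer due are not missing, every later death counts at its own date. At 20% unconfirmed the SAP rule then gives 22.4-28.8%, about 4 to 11 points above 18%. Delaying an event past week 26 keeps the subject event-free at that time.

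**5. Against sampling error.** In 4,000 simulated arms of 25, the SD of the 6-month estimate under the SAP rule is 8.1-9.2 points. On average about 0.5 to 3 subjects per arm are censored at iUPD.

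**6. iDoR.** Protocol 2.3 reports 3 iRECIST responders in Arm IV and 2 in Arm V. If three responders all progress, the steps are 67%, 33% and 0%. Censoring the second moves the median to the third time; censoring the third leaves a plateau at 33%. Such a curve says little under either rule.

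**The case against.** Requiring confirmation is what iRECIST does. Appendix A treats progression as not established until iCPD, so the SAP rule can be defended as a choice of estimand. RECIST 1.1 PFS counts every first progression and is reported beside iPFS, so the two enclose the correct value in the simulation (15.7%, about 18%, 20-25%). SAP 4.9.2.2 has a best-response category of iUPD, and all efficacy data are listed, so many affected subjects can be found. No comparison is planned, and some protocol passages do schedule the second scan.

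Much of this stands, and it is why the point is minor. Three parts do not remove it. Two enclosing curves do not correct the iPFS curve. The iUPD best-response category misses anyone with an earlier iSD, iPR or iCR. The passages that schedule a second scan do not cancel the explicit exemption for unstable subjects.

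A reader might infer more than the documents support:

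- *The primary result or the stage 1 decision is affected.* It is not: ORR, iORR and Go/No Go do not use Table 5.
- *iPFS is grossly inflated.* That needs a large unconfirmed share, and no document gives one.
- *The plan's look at pseudo-progression is spoiled.* SAP 1.4 cites the 7% in comparing ORR under the two criteria; it does not rest on a gap between iPFS and PFS.
- *The interim outputs lack a RECIST 1.1 version.* SAP 5 labels them iRECIST 1.1, which is undefined, and allows further analyses.

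**Conclusion.** The concern holds and is minor. The censoring in SAP 4.9.4.3 and Table 5 is tied to poor prognosis and biases iPFS upward, and iDoR where the subject is a responder. The direction rests on most unconfirmed progressions being real, and it does not change if 7% of them would have resolved.

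The size rests on assumptions: 10-20% unconfirmed, a 9-week median, and scans after progression counted as missing. On these, 6-month iPFS is overstated by roughly 2-7 points, below the SD of about 8-9 points in a 25-subject arm. If unneeded scans are not counted as missing, or all unconfirmed subjects switch therapy, the overstatement at a 20% share is about 4-11 or 9 points. The endpoints remain secondary and descriptive.

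**What to change.** 1. Add a Table 5 row. The first iUPD of an unresolved sequence (no later iSD, iPR or iCR and no iCPD, including iUPD that persists on a repeat scan) is an event at that iUPD date when no further assessment followed and collected data show one of:
   - treatment discontinuation for a disease-related reason, from a list of SAP 4.1 categories fixed before database lock, with at least PD, No longer clinically benefiting and Lack of efficacy;
   - start of new anti-cancer therapy;
   - death.

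   State that this row takes precedence over the new-therapy and two-missed-assessments rows. Keep censoring where confirmation is pending at data cut-off or the subject left for unrelated reasons.
2. State in Table 5 whether scans no longer due after progression count as missing.
3. Report the current rule as a sensitivity analysis, with the number censored at iUPD per arm and the reasons.
4. Reconcile the protocol passages on imaging after unconfirmed progression: synopsis, 5.8, 6.4.1, 6.5, 6.6, 13.2, 13.3 and Appendix A with Table 6. This review takes no position on which is right.

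The cost is SAP wording and programming; the triggers use data already collected. iPFS and iDoR become slightly less favourable, and a stable subject who switches therapy after iUPD counts as progressed. If 7% of unconfirmed progressions would have resolved (20% unconfirmed, 12-week median survival after progression, every unconfirmed case meeting a trigger), true 6-month iPFS is 18.8%. The new row gives 18.2% (0.6 point low); the current rule gives 23.5% (4.7 points high).

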4.9.4.4 Overall Survival

Overall survival (OS) is defined as the time (months) from the date of the first dose date of study drugs to the date of death. Subjects who are alive will have their OS time censored at the last known alive date. The last known alive date will be derived based on the assessment dates that are reported in all CRFs, except for CRFs being used at screening.

Confidential

OS median values and its two-sided 95% CIs will be estimated using KM method. The OS event-free rates at 6 and 12 months if applicable and the associated two-sided 95% CIs will also be estimated using KM method.

OS of each DL in Phase 1b and each arm in Phase 2a will be plotted with KM curve.

